## Available Alternative Opportunities/Treatments

Describe alternative treatments or opportunities that might be available to those who choose not to participate in the study, and which offer the subject equal or greater advantages. If applicable, this should include a discussion of the current standard of care treatment(s).

Patients with acute traumatic cervical SCI are routinely admitted to the ICU for close observation of respiratory and hemodynamic parameters. Particularly for patients with upper-cervical injuries, there is a low threshold for instituting assisted ventilation given their well-known loss of respiratory drive and associated increase in physiologic dead space. Hemodynamic parameters are also carefully monitored in real-time in the neurosurgery ICU via an arterial line (placed per standard-of-care guidelines). For several days after SCI (up to seven days), mean arterial pressure (MAP) measurements are kept ? 85 mmHg to promote optimal perfusion of the spinal cord

and to minimize secondary injury processes. Finally, standard extradural surgical decompression is now widely accepted as appropriate in the treatment of acute traumatic cervical SCI to potentially enhance neurological outcomes (doi: 10.1001/jamasurg.2022.4454). As per standard-of-care guidelines, patients are offered early (? 24h) decompression for acute traumatic SCI when medically feasible and based on individual considerations.

Back to Top

#### Records, Privacy, and Confidentiality

Specify where the data and/or specimens will be stored and how the researcher will ensure the privacy and confidentiality of both. Specify who will have access to the data/specimens and why they need access.

Describe how data will be managed after the study is complete:

- If data/specimens will be maintained, specify whether identifiers will be removed from the maintained information/material.
- If identifiers will not be removed, provide justification for retaining them and describe how you will protect confidentiality.
- If the data/specimens will be destroyed, verify that this will not violate retention policies and will adhere to applicable facility requirements.

If this study will use de-identified data from another source, describe what measures will be taken to ensure that subject identifiers are not given to the investigator.

If applicable, describe procedures for sharing data/specimens with collaborators not affiliated with UK.

For additional considerations: Return of Research Results or Incidental Research Findings HIPAA policies FERPA policies Procedures for Transfer agreements Information regarding multi-site studies NIH Genomic Data Sharing (GDS) Policy Digital Data

The investigative team maintains the right to keep, preserve, use and dispose of the findings of this investigation in accordance with University of Kentucky Records Management and IRB policies and guidelines. Investigational records from this study will be maintained in a confidential manner; subject names will not be associated with any published results.

All clinical information obtained will be considered to be part of the patient's medical chart and will be treated as such according to standard HIPAA guidelines and regulations. Stored electronic data will be stored in encrypted and password protected devices. Binders will be kept in a locked cabinet in the office of the study coordinator. Research records will be maintained at [name]. During and after this study, the subjects' identity will be kept confidential to the extent permitted by law. Patients will be identified by a code, and, except as set forth below, personal information from subjects' records will not be released to any third party without written permission.

The records may be reviewed, by local site personnel, agents of the University of Kentucky, the Institutional Review Board may review the study records including those with identifying information.

Incidental findings: The researchers currently list in the ICF that if they learn of new information in regard to this study, and it might change participant's willingness to stay in this study, the information will be provided to the participant. In addition, findings may be offered to study participants if they meet the following criteria:

a) The finding has important health implications for the participant, and the associated risks are established and substantial.
 b) The finding is actionable, that is, there are established therapeutic or preventive interventions or other available actions that have the potential to change the clinical course of the disease.

c) The test is analytically valid or in the case of imaging, qualified professionals interpret the scan and the disclosure plan complies with all applicable laws. Study investigators will be available to discuss results.

REDCap: REDCap (Research Electronic Data Capture) is a secure web-based application tool used for building and managing surveys and databases used for research, created by Vanderbilt University. Vanderbilt developed a Consortium of institutions to share this research and data capture tool. The Consortium was launched in 2006 and has Consortium partners including the University of Kentucky. The security of the application is largely dependent on the IT infrastructure and environment in which REDCap is hosted, not the software itself. Vanderbilt has a list of best practices that were utilized when installing and hosting the REDCap instance locally. For more information on Consortium Partners, please view http://www.project-redcap.org/consortium.php.

The University of Kentucky REDCap instance was installed in the CCTS & IBI Enterprise Data Center (EDC) in 2008 and is in the Lee Todd, Jr. Building at [name] on the University of Kentucky campus. The web server and the database server are located on separate servers behind a firewall with in-house control with UK's campus network. In addition, in order to maintain secure communications, the web server has a secured security license (SSL) and is located on https://redcap.rdmc.org/redcap/. Research data is stored locally and is backed up daily using MySQL Administrator software using Windows Server software.

REDCap implements authentication of users that log into the system. All accounts are set up using the LinkBlue ID and are password

protected. Furthermore, the software has an auto logout feature included. Once a REDCap user creates a project, they are the owner and have full rights to the project. Once study personnel/users are added by the owner, user rights or privileges are established. User rights can be for view only, edit only, or view and edit. User rights or access can be further limited to individual case forms within the project. Custom locking of case report forms or digital signatures are another feature that can be assigned in the user rights section of the project. REDCap maintains a built-in audit trail that logs all user activity and pages viewed. The logging record can be viewed by those with proper user rights.

Data exportation is defined within the user rights section and can be limited by the project owner as a full data set or as a deidentified data set. Data is exported into comma delimited (CSV) files which can be uploaded into Excel, SAS, SPSS, STATA, or R for analysis. Advanced features of deidentification include removal of free form text, removal of dates, date shifting that keeps the integrity of the date interval, and/or removal of fields tagged as identifiers. REDCap also has an internal email function for large data sets or sensitive data. This feature can be used to send emails to non-REDCap users as well. The file is stored on REDCap and allows nonusers to log in using a secure password to download the files (password to access email is sent in a separate email to the user).

REDCap stores its system data and project information in various relational database tables within a single MySQL database. All data submitted via the web server by the researcher is encrypted while transmitted. The portable devices do not download the data, it is directly stored into the secure web-based connection (https) behind the firewall. This reduces the liability and possibility of researchers losing protected health information. All files are password protected once entered into the system. All project data is stored and hosted locally. No data is ever shared with Vanderbilt or the consortium partners.

REDCap software uses various methods to protect against malicious users that attempt to identify or exploit any security vulnerabilities in the system. In REDCap, all data is intentionally filtered, sanitized, and escaped for every query string data found in the URL while accessing REDCap. Server environment variables that are vulnerable to forgery by users are checked and sanitized. All user submitted data is filtered for any possible harmful mark-up tags (scripts) and then escaped prior to ever being displayed on a web page within the application. SQL queries sent to the database server from REDCap are properly escaped prior to being sent. User defined data used within the SQL query has the data type checked to prevent any mismatching of data types (makes sure a number is really a number). The processes of filtering, sanitation, data type checking, and escaping all help to protect against methods of attacks.

The Consortium has grown to 6506 active institutional partners in 153 countries with 2,400,000 users since 2006. The University of Kentucky currently has over 2500 users with over 5300 projects in production and another 5900 projects in development. All members of the Consortium are active in the future development of REDCap functionality and software testing.

Subject charts, video, recordings, and any other items containing confidential items will be stored in a safe place overnight and not left on the desk. Charts will not be left in an area where others might have access to them. Use of the HIPAA-compliant REDCapTM database management system will be used to store study data. Electronic information will also be stored on OneDrive, Microsoft Teams, UK Healthcare servers, or UK study personnel computers that are password protected and encrypted.

Binders will be kept in a locked cabinet in the office of the study coordinator. Study coordinator will serve to manage theaccess to the information. The study information collected from the subjects' participation in the study will be collected and stored in paper charts and in the REDCapTM database management system.

Any electronic information will be stored behind password/firewall PC and/or encrypted external hard drives. Nerve graft tissue and blood will be collected in coded tubes and stored in a locked facility with limited access.

Summary genomic and medical information may be placed into scientific databases along with data from other research participants. Genomic data and health information would not be labeled with identifiable information. The researchers ask participants/LAR to opt-in/opt-out if they want to provide their consent to sharing tissue samples and health information with other investigators.

UK IRB policies state that IRB-related research records must be retained for a minimum of 6 years after study closure. Do you confirm that you will retain all IRB-related records for a minimum of 6 years after study closure? • Yes < No

### Payment

Describe the incentives (monetary or other) being offered to subjects for their participation. If monetary compensation is offered, indicate the amount and describe the terms and schedule of payment. Please review this guidance for more information on payments to subjects, including restrictions and expectations.

Participants will receive a payment for participating in this study as follows: • \$200 after the Day 182 visit and \$200 after completing the Day 364 visit toward reimbursement for travel expenses.

The total compensation for completing the study will be \$400 provided they undergo the final two study visits. If they receive \$600 or above by participating in research, it is potentially reportable for tax purposes.

Participants will receive a Cash Card at the end of each visit they complete as compensation for that visit.

The information and samples provided by participants will no longer belong to them and might be used in studies that lead to new products for research, diagnosis or treatment. There is no plan to keep participants informed of findings from these studies. These products might have some commercial value. There are no plans to provide financial compensation to the participant should this occur.

### **Costs to Subjects**

Include a list of services and/or tests that will not be paid for by the sponsor and/or the study (e.g., MRI, HIV). Keep in mind that a subject will not know what is "standard" – and thus not covered by the sponsor/study – unless you tell them.

The participants and/or their insurance company, Medicare or Medicaid will be responsible for the costs of all care and treatment they receive during this study that they would normally receive for their condition. These are costs that are considered medically reasonable and necessary and will be part of the care they receive if they do not take part in this study.

Participants or their insurer will be responsible for all costs associated with:

- · SCI (Cervical/Thoracic) assessment done at screening,
- Standard of care surgical management of SCI,
- 2 MRIs performed at screening and Day 2,
- CT scan preformed at screening,
- laboratory tests performed at screening and follow-up visits,
- EKG performed at screening
- · Clinical visits associated with AIS and SCIM assessments

The study-related procedures, and study visits will be provided at no charge to the participant or their insurance company.

Costs associated with treating any injury suffered while participating in this study will be the responsibility of the participants or their insurer. Participants will be advised to ask their insurer if they have any questions regarding their insurer's willingness to pay these costs; this includes contacting Medicare or Medicaid if they are covered by Medicare, or Medicaid.

A co-payment/deductible may be required by their insurer or Medicare/Medicaid even if the insurer or Medicare/Medicaid has agreed to pay the costs. The amount of this co-payment/deductible may be substantial.

#### **Data and Safety Monitoring**

The IRB requires review and approval of data and safety monitoring plans for greater than minimal risk research or NIH-funded/FDAregulated clinical investigations.

- If you are conducting greater than minimal risk research, or your clinical investigation is NIH-funded, describe your Data and Safety Monitoring Plan (DSMP). Click here for additional guidance on developing a Data and Safety Monitoring Plan.
- If this is a non-sponsored investigator-initiated protocol considered greater than minimal risk research, and if you are planning on using a Data and Safety Monitoring Board (DSMB) as part of your DSMP, click here for additional guidance for information to include with your IRB application.

#### 1

All research personnel who work with participants their data or their research samples will have completed training in the protection of human research participants per guidelines issued by ORI. This protocol will receive final approval by the institutional IRB.

The standing independent Data Safety Monitoring Board (DSMB) as chartered by the University of Kentucky Center for Clinical and Translations Science (CCTS) will be used to monitor the safety of this study. The DSMB will review subject recruitment, AE's, side effects, laboratory results, dropouts, protocol violations, and inclusion/exclusion criteria. SAE will be identified by investigators and monitored by the DSMB. The DSMB will meet tri-annually or as needed. More frequent meetings will take place if side effects or other problems are prevalent.

The PI will be responsible for ensuring participants' safety on a daily basis. This protocol will be continuously monitored in real-time by the principal investigator, study team, and study coordinator for adverse events (AEs).

AEs will be graded according to intensity.

- · Mild: Discomfort noticed but no disruption of normal daily activity.
- · Moderate: Discomfort sufficient to reduce or affect normal daily activity.
- · Severe: Incapacitating with inability to work or perform normal daily activity.

The attribution scale for AE reporting will be as follows.

- Definitely There is clear evidence to suggest a causal relationship, and other possible contributing factors can be ruled out.
- Probably: There is evidence to suggest a causal relationship, and the influence of other factors is unlikely.
- Possibly: There is some evidence to suggest a causal relationship.
- Unrelated: AE is judged to be clearly due to extraneous causes and does not meet the above criteria.

The relationship of the AE to DMED +/- ANGI will be specified by the investigators as either unrelated, possibly/probably related, and definitely related. When considering the potential relationship of an AE, the study investigators' assessment will include consideration of the incidence of complications anticipated in the SCI population in the absence of these procedures. For instance, in 485 subjects with acute SCIs recruited into the NACTN database, 1376 total complications were recorded during the initial hospitalization.[11]

The UK reporting categories to the IRB will be used:

• Prompt Reporting of an Unanticipated problem involving risk to subjects or others (including Unanticipated serious or life-threatening AEs) and anticipated or unanticipated research-related deaths to the IRB and Institutional Biosafety Committee. The UK IRB Policy on Unanticipated Problem and Safety Reporting will be followed.

• Continuation Review Reporting if any problems/AEs occurred within 12 months before the continuation review request for a written summary of all problems/AEs involving subjects since the study was initiated, whether anticipated or unanticipated, serious or not serious, life-threatening or not life-threatening, or related or not related to the IRB. The UK IRB has specific reporting requirements for external funding agencies that comply with the requirements of each specific agency.

Monitoring of adverse events. Adverse events will be monitored via exams, vital signs, lab tests, review of subject's medical chart, etc. and documented. Each visit will be documented with a progress note in the research chart.

In addition to presenting a summary of all AEs, where possible, a comparison of AEs occurring in study subjects vs. those occurring in matched historical controls, as captured in the North American Clinical Trials Network (NACTN) registry will be made. To facilitate this comparison, AEs will be grouped into one of 8 systems as reported in the NACTN registry: cardiac, pulmonary, hematology, gastrointestinal/genitourinary, infections, skin, failure of stabilization, and neuropsychiatric.[10, 11] These AEs will be described further with respect to the specific name of the event (that is, the "type" of event; for example, for cardiac events, the type could be bradycardia or other dysrhythmia, cardiac arrest, etc.). Severity ("intensity", as per the NACTN chart) as well as relatedness to the study procedures will also be assessed. The frequency of AEs, as well as mortality (all-cause and system-related), will be compared to that of a matched cohort from the NACTN registry.[10, 11]

All issues of patient care disruption, failure of recording and methodology will be addressed in real-time throughout study period.

Personnel education, missed events, equipment concerns, and care outside trial parameters will be reviewed by Investigators monthly. These data will inform the assessment of feasibility of recordings as per study methodology, and allow for improvements in design for subsequent clinical trials.

Data will be collated and reviewed quarterly throughout the study period. Issues regarding missing data points as well as the potential need for safety-related protocol changes will be discussed with Investigators on an ongoing basis. Interim analysis will be performed yearly with biostatistician support. These analyses will compare study data to historical institutional cohorts. While the study is not powered for endpoint/secondary analyses of motor scores and functional outcomes, the data will be expected to inform power analyses for further study phases.[13]

Back to Top

91630

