#### Please consider these resources: NIH Diversity Policy

#### FDA Diversity Guidance

Number of Participants: To assess the feasibility of recruitment and of the protocol procedures (specifically the = 48 hours injury-to procedure timeframe), the study will plan to enroll and treat 10 patients.

All participants with American Spinal Injury Association (ASIA) impairment scale A or B acute traumatic spinal cord injuries will be assessed for suitability and prospectively enrolled in the study. Either cervical (C2-C8) or thoracic (T1-T12) level injuries in participants aged 18 to 80 years old will be included. Detailed eligibility criteria are listed below.

The use of immunosuppressive therapy (including methylprednisolone and other corticosteroids) will be discouraged; however, use of such therapy will not require exclusion or discontinuation from the study. Of note, the recent Riluzole study reported that corticosteroids were administered at the time of admission to only ~30% of the patients (while 58% of historic NACTN registry patients had received this treatment).[15, 16]

Inclusion Criteria:

- 1. Age: = 18 years and = 80 years
- 2. Written informed consent by patient or legal authorized representative
- 3. No other life-threatening injury
- 4. No evidence of sepsis
- 5. Acute cervical or thoracic SCI with ASIA Impairment Scale grade A or B on admission
- 6. Non-penetrating SCI at neurologic level from C2 to C8 or T1 to T12
- 7. The ability to undergo surgical intervention including study procedures through a posterior approach within 48 hours of injury

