Each of these steps are also at times used in other domains of spinal surgery, specifically oncologic resections. Despite having been demonstrated as an option to manage spinal trauma by Allen over a century ago, [6] these techniques have not been widely studied or applied in modern spinal surgery.

The data obtained from this study will be used to inform and advance the practice of spinal cord decompression and cell-based therapies following acute SCI. Information on microsurgical technique adjustments, neurocritical nursing care standards, medical management, and ISP metrics may prove invaluable in advancing the feasible and safe aspects of these interventions.

SCI is a severely disabling neurological condition leading to impaired mobility, pain, and autonomic dysfunction. As potentially neuroprotective strategies, dorsal myelotomy and expansive duraplasty (DMED) along with cell-based therapies (e.g., autologous nerve tissue graft implantation, ANGI) are recognized as promising candidates to promote functional recovery. However, no trials of these therapies in patients have yet provided reproducible evidence of clinical efficacy, challenged by small effect sizes, low immune suppression, and low sensitivity study designs.

This pilot study design represents the first stage of a systematic evaluation of DMED +/- ANGI performed in the early/acute phase after SCI. Performance of DMED at early timepoints is expected to have the greatest impact on minimizing the deleterious effect of increased ISP and secondary injury due to PHN, which is known to be ongoing over the first hours and days after SCI. Assessment of the feasibility and safety of performing DMED +/- ANGI represent a critical first step prior to engaging in any larger-scale multicenter evaluations of efficacy.

Future larger-scale phases of the study will focus on elucidating the efficacy of these interventions in protecting against secondary neuronal injury processes and in improving function after SCI. The pilot data generated from this study will prove crucial in seeking a larger award from the National Institutes of Health (NIH) and other funding sources.

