## Objectives

List your research objectives. Please include a summary of intended research objectives in the box below.

Specific Aim 1: Assess whether dorsal myelotomy and expansive duraplasty (DMED) after cervical acute traumatic SCI, performed either without or with autologous nerve graft implantation (ANGI), is safe and feasible (n = 5 each)

Safety: Vital signs, clinical examination findings, and clinical laboratory results will be carefully and continuously monitored during the course of hospitalization. Adverse events (AEs) will be assessed throughout the course of hospitalization through Day 28.

Feasibility: To assess the feasibility of running a larger phase II or III study among this population of patients where treatment must begin within the acute time frame. The number of patients who would otherwise be eligible for the study but did not receive study treatment within the 48-hour time frame (ratio of recruited versus screened) and the rate of recruitment (recruited versus eligible) will be recorded. As part of assessing the procedural feasibility, the number of participants who enrolled and received DMED and who received ANGI will be recorded. To assess the compliance feasibility of the study, the number of participants attending each follow-up visit will also be summarized.

Specific Aim 2: Assess whether intraspinal pressure and metabolism can be reliably measured in real-time after dorsal myelotomy and expansive duraplasty, performed either without or with autologous nerve graft implantation (n =5 each). Participants will be monitored in the neurointensive care unit for 7 days or longer (as needed) postoperatively.

Prior to study initiation, ICU personnel will be trained on all study protocols along with the assistance of the nursing manager / educator. Clinical exams, as part of the standard of care, including International Standards for Neurological Classification of Spinal Cord Injury (ISNCSCI) motor scores, will be obtained daily until day 7, then weekly while admitted. ISP will be monitored in real-time with a commercially available indwelling intradural microsensor. [4] Cerebrospinal fluid for microdialysis will be obtained days 1-4, and 7. [3, 12]

Specific Aim 3: Preliminarily assess whether ANGI, in addition to DMED impacts intraspinal pressure and metabolic measurements.

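### AE intensity is graded by discomfort, work and daily activity with no pre-event reference, so it cannot reliably separate mild, moderate and severe events in acute AIS A/B inpatients; the link to the NACTN intensity chart is also unstated.

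*Protocol*

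**What the plan says.** The Data and Safety Monitoring section states that "AEs will be graded according to intensity" and defines three grades:

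- The lowest grade is worded "Mild: Discomfort noticed but no disruption of normal daily activity".
- The middle grade, in paraphrase, applies when the discomfort is enough to cut into everyday activities.
- The highest grade is worded "Severe: Incapacitating with inability to work or perform normal daily activity".

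It does not say what counts as normal for a newly injured participant.

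Entry is limited by inclusion criterion 5: "Acute cervical or thoracic SCI with ASIA Impairment Scale grade A or B on admission". The Background describes the condition in these terms: "SCI is a severely disabling neurological condition leading to impaired mobility, pain, and autonomic dysfunction". Under Objectives, Specific Aim 1 makes safety a primary question and sets the main collection window: "Adverse events (AEs) will be assessed throughout the course of hospitalization through Day 28". Specific Aim 2 puts participants in neurointensive care for at least the first seven postoperative days.

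Further on in Data and Safety Monitoring, where AEs are grouped for comparison with the NACTN registry, the protocol returns to severity. It glosses this as intensity, with the words "as per the NACTN chart) as well as relatedness to the study procedures will also be assessed". The chart is not reproduced.

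**The concern.** An intensity scale has to rank events by how bad they are. This one ranks them by what the participant feels and by what the event takes away from work and everyday life. Someone with an acute severe cord injury, in intensive care after spinal surgery, has already lost most of the second. For events that are silent, or that lie in areas with reduced sensation, the first may not apply.

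Safety is half of Specific Aim 1, and in a ten-participant pilot the description of harms is a main product. If two graders can give the same event different grades and both be following the text, the severity summary says more about the grader than about DMED or ANGI. The grade is assigned when the event is recorded, so no later analysis plan can recover a distinction that the form did not capture.

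The second reference to intensity adds a smaller problem. Staff completing the AE form cannot tell from the protocol whether the three definitions or the NACTN chart governs.

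**Working it through.** No power, alpha or sample-size figure depends on this point. The check is to set the grade definitions against the population, the window and the kinds of event expected.

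**1. The activity anchor, under three readings.**

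- *Literal reading.* Inability to work or carry on everyday activity is largely true of an acute AIS A/B inpatient before any event. Events drift towards Severe.
- *Added effect of the event, against ordinary life.* Little ordinary activity is left to disrupt, so an event can meet the Mild wording because nothing more can be lost. Events drift towards Mild.
- *Added effect of the event, against post-injury status just before it.* The three levels can be told apart.

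Only the third reading works, and the protocol does not instruct it. The first two push grades in opposite directions.

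**2. The discomfort anchor, against events the protocol itself expects.**

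- *How events are found.* Data and Safety Monitoring relies on examinations, vital signs, laboratory tests and chart review. A laboratory abnormality or a change in vital signs may involve no discomfort.
- *Which systems are covered.* The registry grouping includes cardiac events (bradycardia and other rhythm disturbance are the examples given), hematology, infections and skin. Many of these can be silent, and a skin event may lie below the level of sensation.
- *Donor site.* The Background reports that the commonest study-related event in earlier nerve-graft recipients was paresthesia and acute pain at the foot and ankle. The risk section says loss of sensation there is not a concern in this population. A felt-discomfort scale is weak at the one site unique to ANGI.
- *Neurological worsening.* The risk section names bleeding with neurological worsening as a DMED risk. No grade refers to a new deficit on top of an existing severe one.

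**3. The two intensity references.** The three definitions and the NACTN chart appear in the same section and concern the same variable. Nothing states that they are one scale, or which takes precedence. With the chart absent, the documents establish neither agreement nor contradiction.

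**4. Scale, for illustration.** Input: 1376 complications in 485 registry subjects during initial hospitalization (Data and Safety Monitoring).

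- Rate: 1376 / 485 = 2.84 per subject
- Ten participants: 2.84 x 10 = about 28 events
- Each arm of five: 2.84 x 5 = about 14 events

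This assumes that the rate for acute SCI in general applies to an AIS A/B cohort. It counts events that would need a grade. It does not estimate how many would be misgraded.

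**The case against.** The strongest reply is that a grade describes the event, not the participant. No AE exists at baseline to be graded, and a sensible investigator would judge an event against the participant's current state. This stands in part. A reader might infer that every participant already sits at Severe on entry and that the scale carries no information at all. The documents do not support that: the definitions can be read relative to post-injury status, injuries range from C2 to T12, and SCIM is scheduled at Days 84, 182 and 365, which presumes measurable variation in daily function. Preserved sensation may also differ between grades A and B. What remains is that the usable reading is left to the grader.

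A reader might also infer that the definitions contradict the NACTN chart. That cannot be shown, because the chart is not in the document. The wording may mean only that intensity is the chart's term for severity. The supported point is that the link is unstated.

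Nor is participant protection undermined. SAEs are identified by investigators and monitored by the DSMB as a separate matter. Prompt reporting turns on unanticipated problems, serious or life-threatening events and research-related deaths, not on intensity. The sentence specifying the registry comparison names AE frequency and mortality, not intensity, and the list of items for DSMB review does not name intensity either. Events are also described by system, type and relatedness. All of this stands and limits the consequence to the severity data.

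Finally, one could call this a detail for the analysis plan. It is not: the protocol fixes the definitions, and they are applied at the point of recording.

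**Conclusion.** The concern holds in a bounded form. In the main AE window, hospitalization through Day 28, the intensity definitions cannot reliably separate mild, moderate and severe events. Ordinary work and daily activity are already largely absent, many expected events cause no felt discomfort, and no pre-event reference is given. Separately, the two references to intensity in Data and Safety Monitoring must be reconciled.

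The damage is to severity summaries for the Aim 1 safety objective. Its size in misgraded events cannot be computed from the documents. The figure of about 28 events shows only how many grades might be assigned.

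The conclusion rests on one inference: that acute AIS A/B participants in and just after neurointensive care have little ordinary activity left. The protocol's own description of the condition and setting supports this for the acute period. It weakens at later follow-up visits, where function may vary more. The change is worth making before enrolment proceeds, because grades recorded under ambiguous definitions are hard to repair.

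**What to change.** In Data and Safety Monitoring:

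1. Name one governing intensity scale, and refer to it both where grades are defined and where NACTN intensity is mentioned. If the NACTN chart is that scale, reproduce its categories. If not, say how the two relate.
2. Replace the discomfort, work and daily-activity anchors with anchors based on medical consequence (for example, whether intervention was needed) and on change from the participant's own status just before the event.
3. Make every level usable for events without symptoms, such as laboratory, rhythm or skin findings and events below the level of sensation.
4. Keep intensity distinct from seriousness, so that the top level does not merely restate the SAE criteria.

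The cost is protocol wording and an edit to the AE form. No new visits, measurements or staff are needed.
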